#### 4.4.2 Data Collection and Follow-up for Withdrawn Subjects

Even though a subject has withdrawn from the study, it may be important to collect some follow-up or survival data on such subjects throughout the protocol defined follow-up period. Such data is important to the integrity of the final study analysis since early withdrawal could be related to the safety profile of the study drug. If a subject withdraws consent to participate in the study, for subject safety reasons, attempts should be made to obtain permission to collect follow up information whenever possible.

## **5 Study Drug**

### **5.1 Description**

The metformin will be compounded and supplied in 850 mg capsules form by the Mayo Clinic Pharmacy, Research Support.

### **5.2 Treatment Regimen**

Metformin dosing will include a 4 week ramp up of 850 mg po daily prior to starting the BID dose.

### **5.3 Method for Assigning Subjects to Treatment Groups**

The randomization will occur using an envelope system that has been prepared by the statistical department. A series of numbered envelopes will hold the designation of treatment arm. After the subject is consented the next envelope in numerical order will be opened, randomly assigning the treatment arm, by the study team.

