### **5.8.2 Dispensing of Study Drug**

The pharmacy will be notified by the study team of subject enrollment and which arm the subject has been randomized to. They will then dispense the appropriate agent to the subject.

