## **6 Study Procedures**

### **6.1 Visit 1**

The subject will be identified by the Thoracic Surgical Clinics. The study coordinator will consent and enroll the subject. The subject will have a blood sample taken for research.

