### **6.3 Visit 3**

At the time of the subjects follow up (less than 90 days from the time of surgery) the subject will be seen by the study team. Eligibility criteria will be assessed and if the subject is still eligible they will be randomized and receive their study treatment (metformin or observation).

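### The study team that judges eligibility at Visit 3 also opens the randomization envelopes, and no concealment safeguard is described

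*Combined protocol and SAP*

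**What the plan says.** Section 5.3 describes "an envelope system that has been prepared by the statistical department". On the envelopes themselves it says only this: "A series of numbered envelopes will hold the designation of treatment arm". On their use: "After the subject is consented the next envelope in numerical order will be opened, randomly assigning the treatment arm, by the study team".

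Section 6.3 places randomization at the post-surgical follow-up, where "the subject will be seen by the study team". It continues: "Eligibility criteria will be assessed and if the subject is still eligible they will be randomized". Section 5.8.2 then sets the flow of information: "The pharmacy will be notified by the study team of subject enrollment and which arm the subject has been randomized to". Sections 5.4 and 5.7 have the study team hand over the first supply of drug.

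The Study Summary gives a single site and observation as the reference therapy. No placebo product is described, although the Introduction and Sections 3.2 and 7.1 use the word placebo. Section 7.1 compares 2-year RFS by a chi-squared test, with no stratification or covariate adjustment described.

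**The concern.** Randomization protects a comparison only if the people who decide whether and when a subject enters cannot know the next arm. Here one team sees the subject, checks eligibility, opens the envelope and passes the result on. Because the arms are visible, that team also knows every earlier assignment.

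The room for judgement at Visit 3 is limited but real. Section 4.2 excludes subjects receiving adjuvant platinum-based chemotherapy or targeted therapy after resection. That decision falls between surgery and randomization and is plausibly related to stage and prognosis. The date of the visit within the 90-day window is also partly a matter of choice. Section 4.3 recruits from the investigators' own practices, so treating clinicians are close to both decisions.

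If an upcoming arm became known, either decision could be made in its light. The RFS comparison, which Section 2 lists as a primary objective, would then be biased, and an unadjusted test has no means of correcting for that. The adverse event comparison might also be affected.

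**Working it through.** **Roles, set side by side**

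| Step | Who | Where |
|---|---|---|
| Prepares envelopes | Statistical department | 5.3 |
| Keeps envelopes | Not stated | – |
| Sees subject at the eligibility visit | Study team | 6.3 |
| Opens next envelope | Study team | 5.3 |
| Tells pharmacy the arm | Study team | 5.8.2 |
| Hands out first supply | Study team | 5.4, 5.7 |
| Sealing, opacity, registration before opening, opening log | Not stated | – |

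**The plan's own figures.** Section 3.1 randomizes 100 (50 per arm) for 90 evaluable: 2 × 50 = 100 and 90/100 = 0.90, an implied loss of 10%. Alpha, power and effect size are not stated, so the sample size cannot be derived. Nothing below changes it.

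**Illustration 1: prediction from past assignments.** Assume fixed permuted blocks of a size known to the team; the documents mention neither blocks nor size. In a 1:1 block of 4 the last assignment is always certain, and the third is certain if the first two match (probability 1/3). The share known with certainty is (1 + 1/3)/4 = 33.3%. Always guessing the arm with more places left is right (1/2 + 2/3 + 2/3 + 1)/4 = 70.8% of the time.

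| Block size | Certain | Guessed correctly |
|---|---|---|
| 2 | 50.0% | 75.0% |
| 4 | 33.3% | 70.8% |
| 6 | 25.0% | 68.3% |
| 8 | 20.0% | 66.6% |
| 10 | 16.7% | 65.3% |

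**Illustration 2: steering into imbalance.** If k subjects per arm of n = 45 are exchanged between groups whose 2-year RFS differs by g, the difference between arms shifts by 2kg/n. With k = 5 and g = 0.40 (70% against 30%, assumed), this is 2 × 5 × 0.40/45 = 8.9 points. With k = 1 and g = 0.20 it is 2 × 1 × 0.20/45 = 0.9 points. No passage supports any particular k or g.

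**Illustration 3: imbalance into false positives.** Assume no drug effect, 45 evaluable per arm, two-sided 0.05, observation-arm RFS p, and metformin-arm RFS p + d through selection alone. By the normal approximation the chance of a significant result favouring metformin is Φ[(d − 1.96·se0)/se1], where se0 uses the pooled and se1 the separate variances. For p = 0.50 and d = 0.10: se0 = √(0.55 × 0.45 × 2/45) = 0.1049, se1 = √((0.25 + 0.24)/45) = 0.1043, and Φ[(0.10 − 0.2056)/0.1043] = Φ(−1.01) = 0.156.

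| Imbalance d | p = 0.30 | p = 0.50 | p = 0.70 |
|---|---|---|---|
| 0 (nominal) | 2.5% | 2.5% | 2.5% |
| 5 points | 7.3% | 6.9% | 7.6% |
| 8.9 points | 14.1% | 13.2% | 15.9% |
| 10 points | 16.6% | 15.6% | 19.2% |
| 15 points | 31.0% | 29.9% | 39.7% |

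**The case against.** The best defence is that numbered envelopes prepared by statisticians are a workable method for a single-site pilot that lists feasibility first. Section 5.3 requires numerical order, so skipping an envelope would be a protocol deviation. An unpublished block size is what one would want, so silence on blocking is not evidence that the sequence is predictable. In an unmasked trial the pharmacy has to learn the arm from someone. These points stand, and they limit the claim to a lack of separation and of described safeguards.

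A reader might infer more than the documents support:

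- *That the study team holds the envelopes, or that one person does everything.* Custody is not stated, and the study team is a collective.
- *That the next arm can be foreseen.* That depends on opacity, storage and blocking, none of which is described.
- *That steering would leave no trace.* Subjects are enrolled at Visit 1 (Section 6.1: "The study coordinator will consent and enroll the subject") and squamous histology and stage are confirmed at Visit 2. A confirmed subject who is never randomized can therefore be identified, and envelope numbers can be reconciled with randomization order. The plan does not require either check.
- *That most Visit 3 criteria are open to judgement.* Fitness in Section 4.1 means fitness for surgery, stage is confirmed at Visit 2, and the creatinine and 90-day limits are numeric.
- *That feasibility results would be biased.* No between-arm feasibility comparison is planned.
- *That pharmacy release alone is a cure.* It would stop early opening and skipping, but not prediction from visible past assignments.

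**Conclusion.** The concern holds in this limited form. Eligibility assessment at Visit 3 and envelope opening both belong to the study team, the arms are visible, and no safeguard is described that would prevent or detect early or out-of-order opening. Concealment for the RFS comparison therefore rests on the team that decides entry. That the trial is open-label is an inference from the observation arm, but a sound one.

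The size of any bias is unknown. The tables rest on assumed block sizes, numbers exchanged, prognostic gaps and test level; they show why concealment matters and do not estimate what will happen. The change is worth making because selection bias of this kind cannot be reliably repaired at analysis.

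Two related matters are separate. Section 5.3 ties opening to consent, which Section 6.1 places at Visit 1, while Section 6.3 puts randomization after the Visit 3 check; these must be reconciled. Settling the timing would still leave both tasks with the same team. Also, Section 7.1 counts only eligible subjects who started treatment, which allows exclusions after the arm is known and could add to the same bias.

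**What to change.** Amend Sections 5.3 and 5.8.2 as follows.

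1. The research pharmacy or the statistical department keeps the allocation sequence.
2. The study team first records, irrevocably, that the subject is eligible and registered, with identifier, date and time.
3. Only then does the holder release the arm. Each release is logged with date and time, and the log is reconciled with the list of enrolled subjects.
4. If blocking is used, block sizes vary at random and are not disclosed to the study team. This step addresses prediction from past assignments, which third-party release does not.

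The sample size stays at 100 and the analysis is unchanged. The cost is a short procedural amendment, plus the constraint that randomization at Visit 3 must fall within the holder's working hours. Both parties are already involved: the statistical department prepares the envelopes and the pharmacy is told of each enrolment. That no added staff would be needed is an assumption, since the documents say nothing about staffing or cost.

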### **5.4 Preparation and Administration of Study Drug**

The metformin will be prepared by the Mayo Clinic Pharmacy, Research Support. At the time of the visit it will be distributed by the study team. Subsequent refills will be mailed to the subject by the pharmacy. The patient will receive dosing instruction by the study team.

[name], RPh  
Mayo Clinic Pharmacy, Research Support  
[name] or [contact]  
[[contact]](mailto:[contact])

Mayo Clinic Pharmacy, Research Support  
[name] or pager [name]  
[[contact]](mailto:[contact])

### **5.5 Subject Compliance Monitoring**

Subjects will be provided a medication diary in which they should track their administration of the metformin. The study coordinator will make a monthly telephone call to assess the subject's compliance. Subjects who are found to be less than 90% compliant will be counseled in the importance of taking the treatment daily and the PI will be notified.

### **5.6 Prior and Concomitant Therapy**

The subject's medications will be collected and reviewed prior to initiating the metformin or observation therapy to check for prior diabetes treatment. Subjects will be excluded if they are receiving treatment with diabetic agents. During the monthly telephone call the study coordinator will assess for any concomitant treatments with diabetic agents.

### **5.7 Packaging**

The metformin will be packaged by the Mayo Clinic Pharmacy, Research Support. It will be distributed in 3 month increments of drug. The initial doses will be distributed to the subject by the study team. Refills will be sent to the subject by the Mayo Clinic Pharmacy, Research Support via mail.

## **5.8 Receiving, Storage, Dispensing and Return**

### **5.8.1 Storage**

The study agents will be stored by the Mayo Clinic Pharmacy, Research Support under their policies and procedures

### **5.8.2 Dispensing of Study Drug**

The pharmacy will be notified by the study team of subject enrollment and which arm the subject has been randomized to. They will then dispense the appropriate agent to the subject.

### **5.8.3 Return or Destruction of Study Drug**

The remaining study agent will be returned to the study team following 6 months of metformin administration. At the completion of the study, there will be a final reconciliation of drug shipped, drug dispensed, drug returns, and drug remaining. This reconciliation will be logged on the drug reconciliation form, signed and dated. Any discrepancies noted will be documented and investigated, prior to return or destruction of unused study drug. Drug destroyed on site will be documented in the study files.

## **6 Study Procedures**

### **6.1 Visit 1**

The subject will be identified by the Thoracic Surgical Clinics. The study coordinator will consent and enroll the subject. The subject will have a blood sample taken for research.

### **6.2 Visit 2**

The subject will undergo surgical resection as part of their standard of care treatment. Stage IA-IIIA squamous cell carcinoma of the lung will be confirmed. During the surgical resection the patient will undergo collection of tumor tissue, normal lung tissue, and skin biopsies for research.

### **6.3 Visit 3**

At the time of the subjects follow up (less than 90 days from the time of surgery) the subject will be seen by the study team. Eligibility criteria will be assessed and if the subject is still eligible they will be randomized and receive their study treatment (metformin or observation).

### **6.4 Monthly Telephone Calls**

The study team will contact the subjects in the group taking Metformin monthly via telephone to assess drug compliance, adverse events, and any new diagnosis.

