## 2 Study Objectives

Primary objective for pilot study:

1. To evaluate the feasibility of patient randomization, accrual, and tissue collection in a pilot study of metformin versus observation following resection of stage IA-IIIA lung squamous cell cancer for patients.
2. To compare the 2-year recurrence free survival (RFS) rate between metformin and observation.

[figure not shown]
Secondary objective(s) for pilot study:

1. To develop the metformin sensitivity index based on iPS cell lines from the first 20 patients randomized to the metformin arm.
2. To apply the metformin sensitivity index on the remaining 25 patients randomized to metformin and the 45 observation patients (70patients total) to compare the 2-year RFS rate between metformin-sensitive and metformin-not-sensitive patients
3. To compare adverse events between metformin and observation arms using CTCAE version 4.

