### **6.5 Half Yearly Follow Up**

The subjects will be followed every 6 months following surgery for a total of 2 years. At the time of the first 6 month follow up the subjects receiving metformin will return any unused study drug and drug reconciliation will occur.

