## 7 Statistical Plan

### 7.1 Statistical Methods

All patients meeting the eligibility criteria, and who started treatment, will be considered evaluable for the 2 year RFS rate endpoint. The proportion of 2 year RFS rates (along with the 95% confidence interval) will be estimated within each arm by the number of patients who are recurrence-free and alive at 2 years divided by the total number of evaluable patients in each arm, and compared using a chi-squared test.

Clinical data regarding recurrence-free survival (RFS) will be utilized for development of the metformin sensitivity index. Data collected will be summarized using descriptive statistics, including mean and standard deviation and median and inter quartile range for continuous variables, and using frequencies and percentages for categorical variables. Logistic regression models will be used to assess the impact of metformin sensitivity index metrics, treatment, and the interaction between the metformin sensitivity index metrics and treatment on the 2 year RFS status as the outcome of interest.

Adverse events (AEs) will be compared between metformin and placebo using CTCAE version 4. To evaluate the AE profiles associated with each intervention arm, the maximum grade for each type of AE will be recorded for each participant and frequency tables will be reviewed to determine the overall patterns. The number and severity of AEs (overall and by intervention group) will be tabulated and summarized across all grades. Chi-square tests will be used to compare the AE rates between metformin and placebo.

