### **Adverse Event Reporting Period**

Adverse events will be reported after the subject begins taking the metformin or starts the observation period. The bronchoscopy and surgery are considered standard of care.

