## **8.2 Recording of Adverse Events**

At each contact with the subject, the study team must seek information on adverse events by specific questioning and, as appropriate, by examination. Information on all adverse events should be recorded immediately in the source document, and also on the appropriate adverse event worksheet. All clearly related signs, symptoms, and abnormal diagnostic, laboratory or procedure results should be recorded in the source document.

All adverse events occurring during the study period must be recorded. The clinical course of each event should be followed until resolution, stabilization, or until it has been ultimately determined that the study treatment or participation is not the probable cause. Serious adverse events that are still ongoing at the end of the study period must be followed up, to determine the final outcome. Any serious adverse event that occurs after the study period and is considered to be at least possibly related to the study treatment or study participation should be recorded and reported immediately.

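### Monthly adverse-event calls go to the metformin arm only, which biases the between-arm adverse-event test towards more recorded events on metformin

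*Combined protocol and SAP*

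**What the plan says.** Section 6.4 restricts the monthly call to one arm: "The study team will contact the subjects in the group taking Metformin monthly via telephone to assess drug compliance, adverse events, and any new diagnosis". Contact common to both arms is set in section 6.5: "The subjects will be followed every 6 months following surgery for a total of 2 years". Section 8.2 links ascertainment to contact: "At each contact with the subject, the study team must seek information on adverse events by specific questioning".

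Observation patients are meant to be counted. The reporting period in section 8.1 reads: "Adverse events will be reported after the subject begins taking the metformin or starts the observation period". The comparison is a stated secondary objective in section 2: "To compare adverse events between metformin and observation arms using CTCAE version 4". Section 7.1 records each participant's maximum grade per event type, tabulates all grades, and then says: "Chi-square tests will be used to compare the AE rates between metformin and placebo". The control is observation, so the word placebo there is a slip.

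Section 5.6 also mentions a monthly call, to check for diabetic agents. It names no arm for the call and does not mention adverse events.

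**The concern.** If questioning follows contact, and contact differs by arm, the recorded event rate reflects how often patients were asked as well as what the drug did. The protocol's background section expects mainly short-lived gastrointestinal effects. A monthly call will catch such events and a visit six months later may not, so the comparison is most exposed where a drug effect is expected.

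Taking the maximum grade per event type prevents double counting of repeat reports. It does not recover events that were never elicited on observation. Section 7.1 makes no allowance for unequal contact, does not limit the test to severe events and does not state an analysis window.

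The introduction says the pilot is to inform whether a phase III trial is feasible and justified, so a distorted tolerability comparison could carry forward. Feasibility is not affected. Two-year recurrence-free survival status should hardly be affected, because both arms are followed to two years.

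**Working it through.** The plan gives no significance level, event rate or power for this comparison, so there is no figure of its own to reproduce.

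**Contacts.** Sections 6.4 and 6.5 imply 6 calls + 4 visits = 10 enquiries on metformin and 4 on observation, assuming calls end with six months of drug (section 6.4 gives no end date). Within the treatment period it is about 6 to 7 against 1.

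**Inputs from the plan.** Section 3.1 gives 50 randomised per arm and 90 evaluable in all; I use 45 per arm. Visits are timed from surgery, and randomisation is "less than 90 days from the time of surgery" (section 6.3).

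**Assumptions.**
- The true onset probability m per month is the same in both arms: 1%, 5% or 10%. Onset is mid-month.
- The chance of reporting halves every h months until the next contact, with h = 1 or 6.
- A share c of events is recorded without asking: 0, 0.5 or 1.
- The test is the uncorrected chi-square at two-sided 5%.

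**Formula.** P(recorded) = 1 − Π over months of {1 − m[c + (1 − c)·0.5^(delay/h)]}. The rejection rate comes from exact enumeration of two binomials, 45 v 45.

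**Worked case:** six months, m = 5%, h = 1, c = 0.
- Metformin: every delay is 0.5 month, so the monthly term is 0.05 × 0.5^0.5 = 0.0354, and 1 − (1 − 0.0354)^6 = 19.4%.
- Observation: delays are 5.5, 4.5, …, 0.5 months, so the terms are 0.0011, 0.0022, 0.0044, 0.0088, 0.0177 and 0.0354. One minus the product of their complements is 6.8%.
- The test rejects with probability 45.5%, although the true rates are equal.

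**Results with c = 0** (recorded rates are metformin v observation):

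| Window | Onset per month | h = 1: recorded | h = 1: false rejection | h = 6: recorded | h = 6: false rejection |
|---|---|---|---|---|---|
| 24 months | 1% | 8% v 5% | 8.9% | 17% v 16% | 5.7% |
| 24 months | 5% | 35% v 25% | 19.3% | 61% v 59% | 5.7% |
| 24 months | 10% | 58% v 43% | 26.7% | 86% v 83% | 6.5% |
| First 6 months | 1% | 4% v 1% | 6.7% | 6% v 4% | 5.7% |
| First 6 months | 5% | 19% v 7% | 45.5% | 25% v 20% | 10.0% |
| First 6 months | 10% | 36% v 13% | 72.1% | 45% v 36% | 12.8% |

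In the six-month rows at 5% and 10% onset, at least 94% of the false rejections point to more events on metformin.

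**Visit timing.** Visits at months 3, 9, 15 and 21 after randomisation give 19.6% and 5.5% (m = 5%) and 27.4% and 6.7% (m = 10%) over 24 months, so timing hardly matters.

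**Unprompted recording.** With c = 0.5 and m = 5%, false rejection is 11.3% (h = 1) and 6.4% (h = 6) over six months, and 5.7% and 5.5% over 24 months. With c = 1, as for serious events that always reach the record, it is 4.5% to 6.0%.

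**Both arms called monthly.** False rejection is 4.1% to 6.0% in every scenario run.

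**Second model.** Fix the capture probability instead: 0.9 on metformin, true patient-level rate 30%, 45 per arm.
- Observation capture 0.7: recorded rates 27% v 21%, false rejection 10.8%.
- Observation capture 0.5: 27% v 15%, 30.0%.
- Equal capture of 0.9: 4.6% to 5.4% for true rates of 20% to 50%.
- Near-equal capture for severe events (0.95 v 0.90, true rate 10% to 20%): 5.6% to 6.1%.

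At 50 per arm the two unequal-capture results become 10.9% and 31.8%.

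**The case against.** The best counter-argument is section 5.6. It opens by referring to both study arms and then speaks of the monthly call without naming one. If observation patients are telephoned, section 8.2 would require adverse-event questions on that call, and enquiry would be equal during treatment. But section 5.6 does not say they are called, and section 6.4, the section that defines the calls, names the metformin group only. This supports reconciling the two sections; it does not remove the problem.

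The second argument is about size, and most of it stands. Section 8.2 also says: "All adverse events occurring during the study period must be recorded". Read with two years of participation, that makes 24 months the natural window, where the effect is much smaller than over six. The larger figures also need fast-fading recall and no unprompted capture, yet section 9.2 lists hospital and office records as source documents. With half of events captured unprompted, the 24-month rate is 5.5% to 7.0% across all onset rates tried. Monthly onset of 5% or 10% may suit a composite of any event but is high for a single event type. Nothing in the documents selects among these inputs.

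Third, this is a secondary comparison in a pilot, the bias overstates harm rather than hiding it, and open-label reporting bias would remain after any change. All true, but none of it is a reason to add unequal questioning when equal questioning is cheap. A duty to record all events also does not give both arms the same opportunity to report them.

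**Conclusion.** The concern holds. As section 6.4 is written, the arms are questioned unequally, and the named test would be expected to show more events on metformin even if the drug caused none. The direction follows from the text.

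The size does not. Under equal true rates it runs from about nominal (uncommon events, long recall, events recorded unprompted) to 27% false rejection over 24 months and 72% over the first six, the top values requiring 10% onset per month, a one-month recall half-life and no unprompted capture. Mild, transient on-treatment events are the ones at risk, and serious events are little affected. The plan should be changed, but the primary objectives do not depend on it.

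**What to change.** Amend section 6.4 along these lines:

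> The study team will telephone subjects in both arms monthly for the first 6 months after randomisation, using one script on adverse events, new diagnoses and diabetic medication; drug compliance is asked in the metformin arm only.

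This also settles the mismatch with section 5.6. The remaining open-label reporting bias should be stated as a limitation. The cost is at most 50 observation patients × 6 = 300 short calls by the existing coordinator.

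If the calls are not extended, limit the formal between-arm test in section 7.1 to serious or grade 3 and higher events, and report the rest descriptively by arm with the unequal contact schedule stated. That costs only wording, but it gives up a formal test of the low-grade events most expected on the drug. Restricting the test to events elicited at common visits would remove only part of the bias, because metformin patients will already have been prompted monthly.

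In either case, state the analysis window for adverse events (treatment period, full follow-up, or both), and replace placebo with observation in section 7.1 as a wording correction.
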